Descriptive summaries of the observed values and percent change from baseline for each treatment group will also be produced.

Treatment effects over time

A Mixed-effects model with repeated measures (MMRM) will be used for the analysis of continuous endpoints with more than one post-baseline collection time point. All observed data collected during the post-baseline treatment period will be utilized, including follow-up data in order to assess the impact of stopping treatment on the endpoint MMRM analysis will be performed with treatment, study week (nominal timepoint) and treatment-by-study week interaction as fixed effects, and baseline value of the analysis endpoint as a covariate, baseline (SCR2 Eligibility) fibrosis stage (F2/F3) as a factor. If the endpoint being analyzed is log-transformed, the baseline value of the analysis endpoint will also be log-transformed. Repeated measures model with unstructured covariance matrix will be utilized. If this does not converge then compound symmetry structure will be considered. Additionally, the number of covariates may be reduced to improve model fit. Estimates of treatment effects will be assessed using Least Square Means (LSMs) and CIs at each time point. LSM difference for each comparison along with the corresponding 90% CI will be provided. For log-transformed endpoints, the mean relative changes (RC) and their CIs will be exponentiated and percent change will then be determined as follows: Percent change = 100* (RC − 1). If there are major deviations from the statistical assumptions underlying this model then alternative transformations (eg, log) or non-parametric analyses may be presented.

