A MMRM will be used for the analysis of continuous endpoints with more than one post-baseline collection time point. All observed data collected during the post-baseline treatment period will be utilized. The MMRM analysis will be performed with treatment, study week (nominal timepoint) and treatment-by-study week interaction as fixed effects, and baseline value of the analysis endpoint. If the endpoint being analyzed is log-transformed, the baseline value of the analysis endpoint will also be log-transformed. Repeated measures model with unstructured correlation matrix will be utilized. If this does not converge then compound symmetry structure will be considered. Additionally, the number of covariates may be reduced to improve model fit. Estimates of treatment effects will be assessed using LSMs and CIs at each time point. LSM difference for each comparison along with the corresponding 95% CI will be provided. If there are major deviations from the statistical

assumptions underlying this model then alternative transformations (eg, log) or non-parametric analyses may be presented.

Event-based endpoints

The occurrence of hepatic events, and morbidity and mortality and CV endpoints (MACE) over time up to Week 48 will be summarized descriptively by treatment group.

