6.3.6.1. Main Analysis

- Estimand strategy: Not applicable
- Analysis set: Evaluable (Section 4). All randomized participants who take at least 1 dose
 of investigational product who have provided baseline data for the endpoint, and in
 addition have at least 1 evaluable data point post randomization.
- Analysis methodology: A MMRM will be used for the analysis of continuous endpoints
 with more than one post-baseline collection time point. The MMRM analysis will be
 performed with treatment, study week (nominal timepoint) and treatment-by-study week
 interaction as fixed effects, and baseline fibrosis stage (F2/F3) as a factor and baseline
 value of the analysis endpoint as a covariate. If the endpoint being analyzed is logtransformed (i.e. for all percentage changes from baseline in continuous endpoints which
 will be derived from the analysis of log-transformed relative changes from baseline), the
 baseline value of the analysis endpoint will also be log-transformed. Repeated measures
 model with unstructured covariance matrix will be utilized (Section 5.2.2).
- Intercurrent events and missing data: All observed data collected during the postbaseline treatment period will be utilized. Missing data will not be explicitly imputed.

- The sample size, mean, standard deviation, median, minimum, and maximum at the baseline and postbaseline visits for observed values and relative and absolute change from baseline will be presented for each treatment arm.
 - Box and whisker plots by randomized arm and by week will also be displayed to characterize the distribution of percent changes from baseline over time.
- For percentage changes from baseline the model-estimated mean relative changes for
 each treatment comparison and the corresponding 90% CI will be obtained from the
 model. The mean relative changes (RC) and their CIs will be exponentiated and percent
 change will then be determined as follows: Percent change = 100* (RC 1). For
 comparisons of DGAT2i + ACCi BID doses vs corresponding DGAT2i BID
 monotherapy doses corresponding 50% confidence intervals will also be provided.
- CCI
 permit retrospective analysis of CCI
)
 - These results may or may not be generated in the context of the present study.

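### The MMRM omits a baseline-by-week interaction, so its Week 48 estimates may be under-adjusted for baseline on the change scale and lose a little precision

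*SAP*

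**What the plan says.** SAP 5.2.2 (treatment effects over time) lists the mean model as "treatment, study week (nominal timepoint) and treatment-by-study week interaction as fixed effects, and baseline value of the analysis endpoint as a covariate", and adds fibrosis stage as a factor. SAP 6.3.6.1 repeats this for the tertiary and exploratory continuous endpoints, with the baseline "value of the analysis endpoint as a covariate". Protocol 9.4.7 has "treatment-by-study week interaction as fixed effects, and baseline value of the analysis endpoint", without fibrosis stage. No version crosses baseline with week.

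Three other features matter here:

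- **Covariance.** SAP 5.2.2 states "Repeated measures model with unstructured covariance matrix will be utilized", with compound symmetry as the fallback.
- **Follow-up.** The model takes in observed post-baseline data "including follow-up data in order to assess the impact of stopping treatment". For the blood biomarkers this means Week 50, off treatment (SAP 3.3 and 6.3.6).
- **Response scale.** Percentage-change endpoints are "derived from the analysis of log-transformed relative changes from baseline" (SAP 6.3.6.1). Most of the others are analysed as change from baseline.

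For the secondary liver-fat endpoint, SAP 6.2.5.1 uses two routes at Week 48. The Emax dose-response model is fitted to MMRM LS means. The pairwise comparisons come from a separate single-visit ANCOVA.

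**The concern.** The model lets the treatment effect and the covariance differ freely by visit, yet holds the relation to baseline constant across 48 to 50 weeks. For the blood biomarkers it also holds it constant across the end of dosing. A baseline value usually predicts a reading a few weeks later better than one a year later. If so, the early visits have the smallest residual variance and dominate the estimate of the common slope, which then does not fit Week 48.

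At stake is some precision in Week 48 LS means and MMRM contrasts. For liver fat, the Week 48 LS means are the data for the Emax fit of a secondary endpoint. That fit and the ANCOVA also adjust the same endpoint at the same visit with two different baseline slopes.

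**Working it through.** **No figure to reproduce.** The documents give no SD, within-participant correlation or precision target for any MMRM endpoint.

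**Inputs from the documents.**

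- Laboratory visits: Weeks 2, 4, 6, 8, 12, 16, 24, 32, 40 and 48 plus follow-up at Week 50 (SAP 3.5.2, SoA-Table A2).
- MRI-PDFF: Weeks 6, 24 and 48 (SAP Appendix 2.2.1).
- Symptom diary and PROMIS Fatigue: Weeks 12, 24, 36 and 48 (protocol Table 4).
- Sample size: 50 per arm (SAP 2.2). Half are in the imaging substudy (risk table in protocol 2.3), so about 25 per arm.

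**Assumptions.** SDs are equal (set to 1) at all visits. The correlation at a gap of u weeks is ρ(u) = f + (e − f)·exp(−(u − 2)/16), with e = 0.80 to 0.90 at a two-week gap and floor f = 0.40 to 0.60.

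**Formulas.** The visit-specific slopes on the post-baseline value are β_j = ρ(t_j). The residual covariance given baseline is S_jk = ρ(|t_j − t_k|) − β_jβ_k. The large-sample common slope under an unstructured covariance is

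b = (1′S⁻¹β) / (1′S⁻¹1).

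The Week 48 variance ratio, common slope against own slope, is

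1 + (b − β48)² / (1 − β48²),

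and the standard-error (SE) ratio is its square root.

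**Middle case, e = 0.85, f = 0.45.** β48 = 0.45 + 0.40·exp(−46/16) = 0.473, and 1 − β48² = 0.777.

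- Laboratory: b = 0.740. Variance ratio 1 + 0.268²/0.777 = 1.092; SE ratio 1.045.
- MRI-PDFF: b = 0.655. Variance ratio 1 + 0.182²/0.777 = 1.043; SE ratio 1.021.

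**Range over e and f.**

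| Schedule | Variance increase | SE increase |
|---|---|---|
| Laboratory, Weeks 2-50 | 2-17% | 1-8% |
| MRI-PDFF, Weeks 6/24/48 | 1-7% | 0.5-3.5% |
| PROs, Weeks 12/24/36/48 | about 2% or less | about 1% or less |

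If every visit has the same correlation with baseline, b = β48 and the loss is zero. At 25 per arm, a 7% variance increase is worth 25 − 25/1.07 = 1.6 participants per arm.

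**Direction.** The slope for change from baseline is the slope for the value minus 1. In the middle laboratory case the model fits 0.740 − 1 = −0.26 where Week 48 needs 0.473 − 1 = −0.53. For MRI-PDFF it fits −0.35 against −0.53. Both are too shallow, so Week 48 is under-adjusted.

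**Imbalance.** A 0.2 SD chance baseline difference moves the Week 48 contrast by 0.2 × 0.268 = 0.05 SD (laboratory) or 0.2 × 0.182 = 0.04 SD (MRI-PDFF). This is the variance loss seen in one sample, not a second effect.

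**Wider assumptions.** With a constant correlation share of 0 to 0.7, a decaying part with half-life 12 to 48 weeks and 5 to 20% measurement error, the SE ratio ran from 1.001 to 1.15 (laboratory) and 1.001 to 1.09 (MRI-PDFF). Unequal SDs matter too. In one MRI case with ratio 1.054 at equal SDs, the ratio was 1.09 when the SD fell to 0.8 by Week 48, and 1.005 when it rose to 1.5.

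**Simulation.** With 7 arms, complete data and 3,000 runs, SE ratios were 1.045 and 1.007 (MRI-PDFF, 25 per arm) and 1.089 and 1.016 (laboratory, 50 per arm) in a stronger and a milder decay case. Mean contrasts were about zero under both models.

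**The case against.** The strongest reply is that this is a modelling preference of small, conditional size. The documents give no correlations, and the loss is zero if they are stable. Arms are randomized, so a wrong slope costs variance and does not bias the contrast when data are complete. Most MMRM endpoints are exploratory, they are reported at every visit rather than at Week 48 alone, and no hypothesis tests are planned. All of that stands. It limits the size of the point and leaves the omission in place.

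A reader might infer more, in four ways that the documents do not support:

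- **That Week 48 is over-adjusted.** This is how it looks if the post-baseline value is taken as the response (0.74 against 0.47). The SAP models change or log relative change, where the same misfit is under-adjustment. The adjusted contrast and its variance are identical on either scale.
- **That every endpoint spans Week 2 to Week 50.** Only the routine laboratory endpoints do. MRI-PDFF has three visits and the PROs start at Week 12 or later, so the laboratory range should not be quoted for liver fat.
- **That all Week 48 liver-fat contrasts are affected.** The pairwise ones come from an ANCOVA with its own baseline slope (SAP 5.2.2, 6.2.5.1).
- **That the estimates are biased.** Nothing here shows that with complete data. The effect under dropout was not examined.

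**Conclusion.** The point holds as a minor loss of precision. The MMRM has one baseline slope and no baseline-by-week term. When correlation with baseline fades, its Week 48 LS means and contrasts are under-adjusted on the change scale. Under the stated decay assumption the Week 48 SE rises by about 1-8% for laboratory endpoints, 0.5-3.5% for MRI-PDFF and 1% or less for PROs at Weeks 12, 24, 36 and 48. More extreme assumptions reach about 15% and 9% for the first two, and constant correlations give nil. Every one of these sizes rests on assumed correlations and SDs.

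The only secondary result touched is the liver-fat Emax fit. The pairwise liver-fat ANCOVA and the binary primary endpoint are not affected.

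**What to change.** Add the interaction of baseline value with study week to the MMRM in SAP 5.2.2 and 6.3.6.1, and name it for the liver-fat MMRM in 6.2.5.1. Use log-transformed baseline where the response is log-transformed. This would also bring the baseline adjustment behind the Emax inputs into line with that of the Week 48 ANCOVA. Because SAP 5.2.2 allows covariates to be dropped to improve fit, state where this term stands in that order.

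The cost is one extra parameter per visit after the first: two for MRI-PDFF (3 visits) and ten for laboratory endpoints (11 visits). No new data are needed, and almost nothing is lost if the correlations turn out to be stable.

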5.2.3. Analyses for Categorical Endpoints

Not applicable

5.2.4. Analyses for Time-to-Event Endpoints

The occurrence of adjudicated time-to-event endpoints over time up to Week 48 will be summarized descriptively by treatment group.

5.3. Methods to Manage Missing Data

For composite estimands, if a participant discontinues treatment or from the study due to lack of efficacy or toleration prior to Week 48 or if they do not have any evaluable Week 48 Biopsy data, they will be considered to be a non-responder (i.e. response will be imputed as 'non-response'). If they withdraw from the study for other reasons (not related to lack of efficacy or toleration) and have evaluable biopsy data at withdrawal or Week 48, these data will be utilized to determine whether they are a responder or not.

For hypothetical estimands, for the biopsy responder endpoints, analysis will be carried out under the assumption that missing data at Week 48 are missing at random conditional on dose and the strata formed by the covariates., The unconditional estimate of treatment effect will be obtained through covariate adjustment (ie, averaged over strata formed by baseline fibrosis status (F2/F3) and metabolic status (with or without T2DM)). For the continuous endpoint (i.e. percentage change from baseline in liver fat), missing data at Week 48 will not be imputed. MMRM adjusted for covariates will be used to obtain LS mean estimate at Week 48 for each dose, which will then be used in fitting the Bayesian Emax model.

For quantitative biopsy analyses, if the SCR2 Change from Baseline biopsy assessment is deemed to be 'Non-evaluable' the SCR2 Eligibility biopsy assessment will be used instead. If the Week 48 Change from Baseline biopsy assessment is deemed to be 'Non-evaluable', the Week 48 IPV biopsy assessment will be used instead (if this is available, as not all participants had a Week 48 IPV assessment).

Table 10. Handling non-evaluable histological change-from-baseline data

Scenario	Handling
CFB-SCR = nonevaluable (for NAS or fibrosis component(s) required for endpoint)	 Utilize SCR2 eligibility results for whichever component(s) is/are nonevaluable (ie, consensus results if available); if only parallel is available, select results from pathologists that had both the lowest NAS score and/or lowest fibrosis stage Qualitative assessment will only include data from whichever component is evaluable, if any (either NAS components or fibrosis)
CFB-Wk48/DC = nonevaluable (for NAS or fibrosis component(s) required for endpoint)	 If case did not complete IPV → count as non-responder If case completed IPV, utilize Week 48-IPV results for whichever component(s) is/are nonevaluable as Week 48 result in CFB (ie, IPV consensus results if available); if only parallel is available, select results from pathologist that had highest NAS score and/or fibrosis stage Qualitative assessment will only include data from whichever component is evaluable, if any (either NAS components or fibrosis)

Observed cases (including any alternative cases utilized for analysis as described above) will be used when analyzing variables using an MMRM.

For the analysis of safety endpoints, the sponsor data standard rules for imputation will be applied.

PK Concentrations below the limit of quantification

 In all data presentations (except listings), concentrations below the limit of quantification (BLQ) will be set to zero. In listings BLQ values will be reported as "<LLQ", where LLQ will be replaced with the value for the lower limit of quantification.

Deviations, missing concentrations, and anomalous values for PK

In summary tables, statistics will be calculated having set concentrations to missing if one of the following cases is true:

- A concentration has been collected as ND (ie not done) or NS (ie no sample),
- A deviation in visit window is of sufficient concern or a concentration has been flagged anomalous by the pharmacokineticist.

Note that summary statistics will not be presented at a particular visit if more than 50% of the PK data are missing.

Efficacy and Pharmacodynamic (PD) endpoints

- Missing data for all efficacy and PD endpoints will be treated as such and no imputed values will be derived when presenting descriptive statistics at scheduled assessments.
- Concentrations below Lower Limit of Quantification (LLQ) will be set to half-LLQ (ie LLQ/2) for summary outputs; in listings BLQ values will be reported as "<LLQ".
- Derived data by calculation (eg indirect bilirubin) will not follow the rule described above and will be reported as <LLQ (in listings) with a derived value of (<negative value> minus 0.0001 = positive value) when generating summary statistics, as required.
- Any values above the Upper Limit of Quantification (ULQ) will be assigned to the ULQ for display purposes in figures and for computation of summary statistics; in listings ULQ values will be reported as ">ULQ".
- Laboratory parameters that are not correctly collected (eg, collected in non-fasted when required to be collected in fasted state) should not be used and set to missing.

Date of Birth

Only the year of birth is collected in the CRF, therefore the day and the month will be imputed as 01-Jan in order to derive a complete Date of Birth.

6. ANALYSES AND SUMMARIES

6.1. Primary Endpoint(s)

6.1.1. Proportion of participants achieving centrally adjudicated resolution of NASH without worsening of fibrosis or improvement in fibrosis by ≥ 1 stage without worsening of NASH, or both, at Week 48

6.1.1.1. Main Analysis

- Estimand strategy: Composite (Section 2.1.1).
- Analysis set: Evaluable (Section 4). All randomized participants who take at least 1 dose of investigational product who have provided evaluable baseline data for the primary endpoint (i.e. baseline biopsy data).
- Analysis methodology: For assessing dose response, the proportion of responders at Week 48 will be analyzed using a Bayesian Emax dose-response model. For assessing pairwise comparisons, the proportion of responders at Week 48 will be analyzed using logistic regression models with treatment and baseline fibrosis stage (F2/F3) as factors (Section 5.2.1).
- Intercurrent events and missing data: If a participant discontinues treatment or from the study due to lack of efficacy or toleration prior to Week 48 or if they do not have evaluable Week 48 Biopsy data, they will be considered to be a non-responder. If they

withdraw for other reasons (not related to lack of efficacy or toleration) and have evaluable biopsy data at withdrawal or Week 48, these data will be utilized to determine whether they are a responder or not.

- The number and proportion of responders for the primary endpoint at Week 48 will be presented for each treatment arm.
- The model-estimated proportion of responders (and 90% credible interval) for each treatment arm, and the placebo-adjusted proportion of responders for BID each dose (and 90% credible interval), and odds ratio and risk difference (and corresponding 90% confidence interval) for other treatment comparisons will be presented at Week 48. For comparisons of DGAT2i+ACCi BID doses vs corresponding DGAT2i BID monotherapy doses corresponding 50% confidence interval will also be provided.

6.1.1.2. Sensitivity/Supplementary Analyses

Sensitivity Analyses

In order to assess the sensitivity of the dose Bayesian Emax dose-response model to the location and informativeness of the prior distributions, sensitivity analyses may be performed that will utilize alternative prior distributions.

Supplementary Analyses

An analysis that assesses the primary endpoint using a hypothetical estimand strategy (Section 2.1.3) will be performed. Using a hypothetical estimand strategy in the study population of randomized and treated participants with biopsy-confirmed NASH and fibrosis, as assessed by the sponsor-identified central pathologist(s), the treatment effect of DGAT2i doses administered alone and coadministration of DGAT2i + ACCi relative to placebo, and coadministration of DGAT2i + ACCi, relative to DGAT2i alone will be estimated, in terms of estimating the proportion of 'clinical responders', defined as participants achieving centrally adjudicated: resolution of NASH without worsening of fibrosis or improvement in fibrosis by ≥1 stage without worsening of NASH, or both, at Week 48, assuming all patients had remained in the trial and received treatment as planned without withdrawal up to 48 weeks. All treatment effect contrasts will be obtained through fitting the Bayesian doseresponse and/or exposure-response models with a logit transformation, or logistic regression models.

Additional analyses may also be performed to assess participants whose SCR2 assessment when as part of the final paired biopsy assessment was different to the original SCR2 assessment for eligibility. Summaries of proportion of participants with No Change, Improvement or Worsening in each component of NAS and Fibrosis from the qualitative comparison of baseline to the end of treatment biopsy results will be provided. Shift tables of Baseline/SCR2 vs Week 48/EOT individual NAS component scores and fibrosis grades will be produced. If a participant doesn't have a pair of CFB results (for SCR2 and Week 48/EOT) (even after assessing if other possible results are able to be utilized as described in Table 10), then their SCR2 Eligibility result will be tabulated vs a 'Missing' Week 48 result.

To assess concordance of intra-pathologist reviews, a random sample of biopsies will be selected (10% for each of the screening biopsies amongst those ultimately randomized and a separate 10% for the end of treatment biopsies obtained) to be reviewed again by the 2 central pathologists (i.e. IPV review) — with the review process identical to that used for SCR2 eligibility. Kappa statistics (simple and weighted) and 90% CI will be estimated based on the initial and second assessments of each central pathologist. For the screening biopsy comparisons, the SCR2 Eligibility biopsy will be the initial assessment that is compared the second assessment. For the Week 48/EOT biopsy comparisons, the Week 48/end of treatment biopsy from the Blinded side-by-side (Change from Baseline) assessment will be the initial assessment that is compared the second assessment. Concordance of inter-pathologist reviews (Pathologist 1 vs Pathologist 2) will also be assessed for Baseline/SCR2 and Week 48/EOT separately. In addition, summaries of the proportion of biopsies at each visit that had to undergo consensus review and a summary of screening biopsies that remaining eligible when reviewed as part of the CFB assessment will be produced (by treatment group).

